Collection DT	Specimen	Test Name	Result	Units	Ref Range
01/18/2022 09:20	BLOOD	PSA	0.600	ng/mL	0 - 4
03/03/2022 08:00	BLOOD	PSA	0.200	ng/mL	0 - 4
06/25/2022 10:15	BLOOD	PSA	<0.100	ng/mL	0 - 4

ADT injections in the last 12 months:

Rx #	Stat	Qty	Issued	Last Filled	Rem
LEUPROLIDE (ELIGARD) 22.5MG(3 MONTH) LA INJ					
12824236	ACTIVE/SUSP	1	06/25/2022	06/25/2022	(1)

For this clinical scenario, where the harms of ADT likely outweigh the benefits, NCCN (tinyurl.com/2p9f5w8r) and AUA guidelines (tinyurl.com/4ueptrtd) recommend either transitioning to intermittent ADT or discontinuation of ADT.

Talking points:

-We are learning more about prostate cancer all the time, and continue to update recommendations based on new information. Since hormone therapy comes with long-term effects on your health, I'm worried the harms are greater than the benefit.

-Hormone treatment can have long-term effects that you don't notice right away, like thinning bones, diabetes, and heart disease. Most patients don't notice these conditions until they have a complication like a broken hip.

-If we get any indication that your prostate cancer is behaving more aggressively or causing you problems, we may decide the benefits of hormone therapy are greater than the harms. We can restart the hormone therapy at any point.

Patient information sheet - "Living Well with Prostate Cancer: Is Hormone Therapy Still Right for You?"

tinyurl.com/bdh45bnn

Patient prefers to:

Continue ADT

OR

Discontinue ADT and follow up in 3-6 months with a PSA test

Updated 7/27/2023 – changes made to information displayed in the ADT injections section.

Advisory: ADT for Localized/Non-Metastatic Prostate Cancer

Based on multidisciplinary review, this patient appears to be on ADT as treatment for biochemically recurrent prostate cancer.

Most recent PSA values:

Collection DT	Specimen	Test Name	Result	Units	Ref Range
06/20/2023 09:54	SERUM	PSA	0.19	ng/mL	0 - 4
11/05/2022 09:22	SERUM	PSA	0.57	ng/mL	0 - 4
08/16/2021 09:16	SERUM	PSA	1.06	ng/mL	0 - 4

ADT injections in the last 12 months:

LEUPROLIDE (ELIGARD) 45mg given SQ in Right side of abdomen Administered 06/20/2023
Expiration date / Lot#: [mmm]/[yyyy] Lot [xxxxxx]A1

LEUPROLIDE (ELIGARD) 45mg given SQ in Left side of abdomen 11/05/2022
Expiration date / Lot#: [mmm]/[yyyy] Lot [xxxxxx]A1

LEUPROLIDE (ELIGARD) 45mg given SQ in Right side of abdomen 08/16/2021
Expiration date / Lot#: [mmm]/[yyyy] Lot [xxxxxx]A1

For this clinical scenario, where the harms of ADT likely outweigh the benefits, NCCN (tinyurl.com/2p9f5w8r) and AUA guidelines (tinyurl.com/4ueptrtd) recommend either transitioning to intermittent ADT or discontinuation of ADT.

Talking Points:

-We are learning more about prostate cancer all the time, and continue to update recommendations based on new information. Since hormone therapy comes with long-term effects on your health, I'm worried the harms are greater than the benefit.

-Hormone treatment can have long-term effects that you don't notice right away, like thinning bones, diabetes, and heart disease. Most patients don't notice these conditions until they have a complication like a broken hip.

-If we get any indication that your prostate cancer is behaving more aggressively or causing you problems, we may decide the benefits of hormone therapy are greater than the harms. We can restart the hormone therapy at any point.

Patient information sheet - "Living Well with Prostate Cancer: Is Hormone Therapy Still Right for You?"

tinyurl.com/bdh45bnn

Patient prefers to:
Continue ADT

OR

Discontinue ADT and follow up in 3-6 months with a PSA test

PILOT CLINIC AND ADT PROVIDER ASSESSMENTS

- For the pilot, we will ask the Site Champions/Study Consultants to test the assessment surveys and provide feedback to help refine the survey and implementation procedures for the cRCT.

PILOT DATA COLLECTION

- Feedback from Site Champions/Study Consultants regarding pilot site implementation will be collected informally during study meetings.
- The organizational assessment survey will be fielded to Site Champions/Study Consultants and refined throughout the pilot.
 - Outcome measures in Table 4 will be assessed and approaches to ascertainment, tracking, and analyses refined during the pilots.
- Outcomes will be collected from VA CDW/Cancer Registry/Vital Status/CMS records and CPRS/Capri/JLV/WebVRAM for all clinic visits documented as providing low-value ADT at baseline, 3 and 6 months.

INSTRUCTIONS FOR PHONE FORWARDING AND VOICEMAIL

Study Contact Information is the designated study phone in [name]'s office: [contact].

Phone Forwarding

The instructions for forwarding will depend on the phone, but for the ones currently in the office:

- 1) Select a line and press **FORWARD ALL**
- 2) Dial the number that you want to forward to

[figure not shown]
To deactivate, press **FORWARD OFF**

Checking Study Voicemail

- 1) Dial study phone number (from jabber or any phone)
- 2) Once voicemail starts, select *
- 3) Instruction's state: "Enter your ID followed by pound" enter phone number: **xxxxx#**
- 4) Instruction's state: "Enter your pin followed by pound" enter pin: **xxxxx#**

(Note: PIN #'s are required to be changed often, study staff will add a 1 to pin each time it needs to be updated.

PILOT STUDY FLOW CHART

PILOT RANDOMIZED IMPLEMENTATION TRIAL

TRIAL SITE SELECTION

- We will update national VA and Medicare data to identify eligible sites for the cRCT.
- All VA sites with high rates of low-value ADT from 2020 – 2022 will be considered eligible to participate in the study.
- We will start with the 40 facilities with the highest rates of low-value ADT and continue down the list as necessary.
- We will exclude sites requiring translated materials (e.g., Puerto Rico).
- If feasible, we will exclude sites scheduled to transition to Cerner prior to the end of the cRCT.
- We will randomize 4 VA facilities with high rates of low-value ADT use.

TRIAL SITE RECRUITMENT & RANDOMIZATION

- The top 4 sites with high rates of low-value ADT use and meeting above criteria will be invited to participate in the study.
- All invited sites that agree to participate will be included.
- We expect 80% participation by eligible sites.
- If sites are unwilling or unable to participate, we will continue down the list of sites until we reach a maximum of 4 participating sites.
- Study staff will send an email from the study Co-PI to Urology Chiefs to recruit as Site Champions.
 - If we are unable to contact Urology Chiefs, or if we do not receive a response from the Urology Chief after two formal email contacts, we may reach out to the Chief of Surgery, Chief of Med/Onc, or Chief of Rad/Onc (and copy the ACOS/R) about serving as Site Champion.
 - If the Urology Chief declines to serve as Site Champion, we may ask if they have any suggestions for an alternate designee.
 - In the event we are unable to recruit a Site Champion, all Site Champion communications will come from the study team.
- Once Site Champions have obtained approval from the MCD, each site will be randomized to the **Or** or **Sc** arm. The Data Manager will work with our Consultant, [name] on randomizing sites.
 - Our current plan will be to stratify sites by availability of Radiation Oncology to ensure there is an even distribution of Radiation Oncology in both intervention arms. We intend to randomize sites in blocks of 2-4.
- Once site Clinical Health Information Officer has agreed to implementation the intervention at their site, study staff will apply for site CPRS access.
 - Note: Once you have CPRS access for a site, set an Outlook reminder to log in to each site every 30 days.

TRIAL OR/Sc IMPLEMENTATION

- Implementation procedures will be similar to those of the pilot but refined as needed based on pilot outcomes and needs specific to trial site implementation.
- Interventions will be implemented for up to 12 months at each site.
- Study staff will apply for CPRS access at each site once we receive approval from either the Medical Center Director or Site Champion.
- Baseline ADT Prescribing Meetings – these meetings with Site Champions or their designees will not be mandatory for the RCT. We will move forward with our trial implementation even if we haven't collected information regarding the ADT ordering process.

- Implementation Education Session (IES) – to make scheduling easier on the study team, we may implement one IES per site instead of each department. We will move forward with implementing the interventions after scheduled IES's, even if they have been cancelled.
- There is a possibility that patients will receive ADT injections more than once during the intervention period. If this is the case, then the intervention will be triggered more than once for the same patient.

TRIAL DATA COLLECTION

- Data sources for our primary, implementation and secondary fidelity outcomes will be refined during the pilot. Data collection and outcomes analyses plan will also be further developed during the pilot.
- We will likely assess **Or** fidelity using informatics data generated through the ordering process.
- We will use chart review to identify **Sc** documentation in the EMR, in addition to other informatics approaches.
- We will match our 4 intervention sites with up to 8 control sites with comparable departments and numbers of patients. We will complete chart reviews for control sites twice. The first review will look at ADT injections at the start of the intervention for the matching intervention site(s) to confirm whether patients would have been eligible at the intervention launch site we are not looking after the date the intervention started. The second review will occur again at the end of the 6-month intervention period for the matching intervention site.
- Providers and Site Champions at participating facilities will be asked to complete anonymous assessments in Qualtrics at baseline and 1-month post-intervention.
- We will examine relationships between survey and trial outcomes in exploratory analyses to assist with understanding the generalizability of our findings.

TRIAL CLINIC AND ADT PROVIDER ASSESSMENTS

- We will obtain national Union review for conducting assessments. For the crRCT, Site Champions and providers will be invited to complete the surveys (Appendix VI). The Ann Arbor Study Team will revise the survey as needed based on piloting feedback and outcomes.

The Site Champion Clinic Assessment

We will administer surveys to our Site Champions upon MCD approval. Survey data will be collected anonymously via VA Qualtrics. The survey includes questions about ADT ordering and clinic practices; the survey should take about 5 minutes to complete.

- We will ask Site Champions to complete a survey at baseline. The exact timing of the survey will be decided during the pilot testing period.

The ADT Provider Assessment

We will administer surveys at baseline and 1-month post-intervention period to ADT prescribers. Survey data will be collected anonymously via VA Qualtrics. The survey includes questions about ADT ordering and clinic practices; the survey should take about 5 minutes to complete.

- Baseline survey - we will ask providers to complete the baseline survey during the IES's. Providers will be able to access the survey by scanning a QR code on their phone (code will be available in the IES PPT), or via a link the study team will enter in the Zoom meeting chat.
- 1-Month post-intervention survey – at the end of the intervention period, we will email providers with a link to the follow up Qualtrics survey.

RECORDS CONTROL AND DISPOSITION

- At the study's conclusion, all personally identifying information (PII) will be moved to an access restricted folder on the Ann Arbor VA OI&T network, accessible only to the HSR&D data manager.
- Members of the study team will no longer have access to these data.
- Data will be destroyed by the data manager according to RCS 10-1, 6 years following the end of the fiscal year after completion of the research project.
- All research data will be presented in aggregate form only.
- Publications from this research will be made available to the public through the National Library of Medicine PubMed Central website within one year after the date of publication.
- Prior to final data disposition according to RCS 10-1, deidentified final data sets underlying all publications resulting from the proposed research will be shared outside VA. Members of the scientific community who would like a copy of the final data sets (i.e., data sets underlying any publication) from this study can request a copy by e-mailing [name] at [contact]. They should state their reason for requesting the data and their plans for analyzing the data. Final data sets will be copied onto a CD. The CD will be sent to the requestor via FedEx. Each data set will be accompanied by documentation that lists all variables described in the publication and links them with variable names in the data set. De-identified data will be provided after requesters sign a Letter of Agreement detailing the mechanisms by which the data will be kept secure and access restricted to their study team. The agreements will also state the recipient will not attempt to identify any individual whose data are included and will not share the data with anyone outside of their research team. The dataset will not include PII and all dates will be changed to integers to allow for calculation of time periods.

APPENDICES

- I. Letters of Support from Site Champions/Consultants
- II. Pilot Email Templates
 - Template Email to MCD
 - Template Email to Pharmacy Chief
 - Template Email to Clinical Department Chiefs
 - Template Emails to CHIO/CACs
 - Template email to Providers
- III. RCT Email Templates
 - Template Email to Recruit Site Champion
 - Template Emails to MCD
 - Template Email to Pharmacy Chief
 - Template Email to Clinical Department Chiefs
 - Template Email to Providers
 - Template Emails to CHIO/CACs
 - Template Emails to Providers
- IV. Patient Dashboard Example
- V. Clinic Handout
- VI. cRCT Organizational Assessment(s)

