Effectiveness *** (primary implementation outcome, and primary outcome of trial)	Low value ADT (LVADT) prescription order decrease $(\text{LVADT candidate expected orders} - \text{LVADT not ordered}) / (\text{LVADT got order} + \text{LVADT stopped order})$	
Adoption (provider level)	At least 1 order fired and signed (provider level)	At least 1 script signed (provider level)
Penetration Adoption (order level)	$(\# \text{ times order entry justified}) / (\# \text{ times order went through anyway})$	$\# \text{ scripts signed} / (\text{LVADT got order} + \text{LVADT stopped order})$
Implementation	Did implementation vary? 
- Differential adoption/penetration in medical oncology vs radiation oncology vs urology- Measure adoption/penetration at different time points (e.g., 3/6 months)- Number of sites that withdraw from participation (e.g., 3/6 month withdrawal rates)	
Fidelity	
- Were the justifications appropriate? (i.e., was something entered, or was no reasoning put in (enter n/a, etc))	
- Was the script edited? (i.e., not just signed)
Maintenance (site/setting level)	Proportion of sites that would elect to continue intervention, if available	

TIMELINE

R37 Funding: 1/1/2022 – 12/31/2023

PILOT SITE SELECTION

- The **Or** and **Sc** interventions will be piloted at the study PI and consultants' sites as follows:

Site	Site Champions	Intervention
VA Ann Arbor Healthcare System	[name] (co-PI)	Or & Sc
VA Greater Los Angeles Healthcare System	[name]	Or
VA New York Harbor Healthcare System	[name]	Or

PILOT SITE IMPLEMENTATION OVERVIEW

- Drs. [name], [name], and [name] are all consultants who have agreed to serve as Site Champions for the pilot work.
 - Study consultants do not have access to identifiable data or the study folder and are not "engaged" in study activities.
- Pilot sites will not be randomized.
- The ADT Order Check Attestation Intervention (**Or**) will be implemented at all sites, as this intervention requires engagement with other services, such as CAC, pharmacy, etc., and its procedures are most in need of refinement.
- The ADT Provider Script Intervention (**Sc**) will be implemented at Ann Arbor.
- The official start date for the pilot begins when we have started adding HF's and/or assigning progress notes. Pilot sites will be followed for up to 6 months.
- Facility Notifications & Approvals

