- Study staff will enter a CPRS progress note approximately one business day prior to a target low-value ADT clinic visit. Notes will not be assigned for ADT injection-only visits. The note includes talking points for the provider to help with a discussion with the Veteran.
 - The note can be edited and signed by the provider, giving a quick and simple way to document the discussion. The progress note will prompt providers to indicate whether patient prefers to continue or discontinue ADT.
- The progress note will include links to the clinic handout which will be posted on CCMR's external website (outside VA firewall).
- Providers may modify, ignore, or delete the progress note.
- Appropriate use of the indication will be tracked for fidelity. We will track how many notes are placed. We will also be able to run a report of all signed and unsigned progress notes.
- At the end of the intervention period, Ann Arbor CAC's will delete/remove all unsigned progress notes. Unsigned notes will need to be reassigned at the end of the study. [name], or another AAVA CAC will run a report of unsigned notes by our note title for Ann Arbor. The CAC will change the note author back to a member of the study team, which we can then remove from CPRS. We will ask the Data Manager to reassign the note in CDW for other sites or ask the site CAC if necessary.
 - If providers delete an unsigned note, it's unlikely to appear in a TIU progress note report.

CLINIC HANDOUT

- The clinic handout will be tailored to each individual facility, e.g., with site name (Appendix V).
- Prior to each site's scheduled IES, study staff will provide clinic handouts to the clinic point person identified by the Site Champion (the clinic point person may also be the Site Champion). We may use one or more of the following approaches:
 - By mail: hardcopies of the handout will be mailed to the clinic point person (as requested). Each clinic will receive 50 copies of the handout.
 - By email: copies of the handout will be emailed to clinic point person (this may happen when we send Site Champions the email templates or in a separate email). Each clinic will be instructed to print 50 copies of the handout.
 - By website: a copy of the handout will be accessible on CCMR's website (outside the VA firewall). A link to the website will be included in the progress note.

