Outcomes  Not Eligible  Eligible - added HF  Eligible - assigned note  Eligible - no intervention																																						
																																						

Important Notes:

1. *Check the database every morning to determine if a progress note needs to be assigned for an appointment the following day.
2. If a note is mistakenly assigned to the wrong provider, or for a patient who is ineligible, notify [name] and [name] immediately.
3. Provider transitions – If you need to assign notes for eligible patients whose ADT prescriber is no longer in CPRS (and there's no other indication of who patients will be meeting with for their upcoming appointment), ask Site Champion if they wish to have those notes assigned to them or transfer them to another provider on our list.
4. **When selecting note from CPRS "Progress Note Properties" box, you will see two notes with the same title in the list. It's not a duplicate note, it's a quirk of CPRS that displays the note twice. It has to do with how more titles are created and that note titles can have a print name that is different. Whenever we create a note title, it creates 2 lines in CPRS that make it look that there are two titles but there's only the one. You may select either note with our title.
5. Do not assign notes for ADT injection-only visits.
6. Once you have assigned this unsigned progress note to an author that isn't yourself, only that person will see this unsigned progress note in CPRS. Notes signed by the author will be visible to everyone in CPRS.
7. If you try to select a new patient or exit CPRS with an unsigned note, it will prompt you to see if you want to sign it or proceed and delete it.

8. If you accidentally select "Add Chart Review" in the patient form in the database, thereby creating a new duplicate record, just go into the table and find the row that's the duplicate and delete it.

CPRS PROVIDER PROGRESS NOTE TEMPLATE

Available in AAVA CPRS: Shared template>> ZZ considered>>[name] test>>prostate study note

Mock data (dates, results, etc.) shown in note

Original Template Version

Advisory: ADT for Localized/Non-Metastatic Prostate Cancer

Based on multidisciplinary review, this patient appears to be on ADT [as primary therapy for] or [as treatment for biochemically recurrent] prostate cancer.

Most recent PSA values:

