APPENDIX VI: cRCT ORGANIZATIONAL ASSESSMENTS

Living Well Prostate Cancer Survey – Site Champion Clinic Assessment

Thank you for your willingness to participate in this survey supported by the NIH National Cancer Institute (PI: [name]/[name]; R37CA2228).

We are interested in learning more about the role of androgen deprivation therapy (ADT) in the management of prostate cancer patients in your clinic.

Your participation in this survey is purely voluntary and you may choose not to answer any questions. This is an anonymous survey, meaning we will not collect any personally identifiable information from or about you. Results will be reported in aggregate in any reports.

This 4-question survey should take about **5 minutes** to complete.

Click the **Next** button to continue.

Q1. Please indicate your clinical specialty from the list below:

- Urologist
- Medical Oncologist
- Radiation Oncologist
- If other, please specify:

Q2. For patients with prostate cancer in your practice who are **currently on ADT**, please complete the following table:

How often do the following types of providers order ADT in the electronic medical record for these patients?

	Not Applicable	Never	Sometimes	Most of the time	Always
I order ADT for my patients					
Urology					
Medical Oncology					
Radiation Oncology					
Nurse Practitioner/Physician's Assistant					
Resident/Fellow					
If other, please specify: 					

Q3. For patients with prostate cancer in your practice who are **currently on ADT injections**, **when is the order for ADT written?**

Day of injection	
1 day before injection	
2-7 days before injection	
More than 7 days before injection	

No consistent pattern or unknown	
----------------------------------	-----------------------

Q4. For patients in your clinic **currently on** ADT injections for prostate cancer, **how often do they typically receive** the following?

	Unsure	1 month	3 months	6 months	12 months	Other time interval
ADT injection						
PSA level blood test						
Clinic visit for prostate cancer						

Living Well Prostate Cancer Survey – ADT Provider Assessment Tool (Baseline, 1 month post-intervention completion)

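### Sc penetration in Table 4 divides visit-based notes by low-value orders, so unless every order is tied to a discussion visit it mixes provider uptake with the local injection schedule

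*Protocol*

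**What the plan says.** **Delivery of the script.** The Progress Note part of the Provider Script (Sc) Intervention section has study staff enter the note "approximately one business day prior to a target low-value ADT clinic visit". It then states: "Notes will not be assigned for ADT injection-only visits". The Important Notes under the CPRS instructions for Sc repeat this to staff: "Do not assign notes for ADT injection-only visits".

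**Injection-only visits exist.** The same CPRS instructions show two example appointment titles carrying the prefix used for Columbia. One is marked as an ADT discussion and the other, a nursing appointment, as injection only. Columbia is one of the two trial sites for which note-assignment steps are written.

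**The measure.** In Table 4 the row beginning "Penetration Adoption (order level" gives, for Sc, the number of scripts signed divided by the sum of low-value ADT orders given and low-value ADT orders stopped. Neither order count is defined, and nothing removes orders that could not have had a note. The order-check (Or) column of the same row uses a different base: orders justified over orders that went through anyway.

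**Repeat exposure.** Trial Or/Sc Implementation notes that a patient may receive more than one injection during the intervention period, and continues: "If this is the case, then the intervention will be triggered more than once for the same patient". It does not distinguish the arms.

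**The concern.** The numerator can arise only at a discussion visit, whereas the denominator counts orders. In the Or arm these units coincide, because the check fires when the order is placed. In the Sc arm they need not. A patient who sees the prescriber occasionally and a nurse for the injections in between may generate several orders, only some of which could have been preceded by a note.

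Penetration exists to show whether providers took up the tool. If a site's Sc figure is low because many of its injections are given at nursing appointments, the number looks like poor uptake although the protocol itself withheld the note. In a trial with four randomized sites, differences between local schedules could be mistaken for differences in acceptance of the script, and that reading would carry into the design of a larger trial.

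**Working it through.** The protocol gives no penetration value to reproduce, so the check evaluates the Table 4 formula under perfect delivery: every note that may be placed is placed, and every placed note is signed. A measure of uptake should then equal 100%.

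**Inputs**

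- Injection interval: 1, 3 or 6 months (Identifying Low-Value ADT in Pilot, Chart Reviews).
- Window: 6 months, the time point of the primary outcome.
- Number of discussion visits: an assumption. The protocol fixes no visit interval. The Site Champion survey in Appendix VI asks about injection interval and clinic-visit interval as separate items.
- One order per injection: an assumption. The protocol does not say how many injections an order covers.
- ADT continued throughout the window: an assumption.

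**Formula under these assumptions**

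Penetration = discussion visits in the window / (6 / injection interval in months)

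| Injections | Orders in 6 months | Discussion visits | Ratio with every note signed |
|---|---|---|---|
| Monthly | 6/1 = 6 | 1 | 1/6 = 17% |
| 3-monthly | 6/3 = 2 | 1 | 1/2 = 50% |
| 3-monthly | 6/3 = 2 | 2 | 2/2 = 100% |
| 6-monthly | 6/6 = 1 | 2 | 2/1 = 200% |

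The last line needs one more condition: a note is assigned and signed at a discussion visit when no order is due, and that visit adds nothing to either order count.

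**General ceiling.** Let s be the share of orders tied to injection-only visits, with one note for each remaining order. The highest attainable value is 1 - s:

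- s = 25%: 75%
- s = 50%: 50%
- s = 75%: 25%

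**Sensitivity to the assumptions**

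- If one order written at a discussion visit covers both 3-monthly injections, the 50% becomes 1/1 = 100%.
- If the first signed note leads to stopping, and this is counted as a single stopped order, the ratio is again 1/1 = 100%.

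**Alternative measure.** Notes signed over notes assigned gives 1/1 or 2/2, that is 100%, in every line of the table.

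**The case against.** The strongest reply is that the denominator is undefined rather than wrong. An order given or stopped could mean one per injection, one decision per discussion visit, or one outcome per candidate patient. The mock note's prescription line has a column that appears to show a remaining fill, so one order may cover more than one injection. This stands. A reader might infer that injection-only orders are certainly counted, but the documents show only that nothing excludes them.

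Four other stronger readings are also unsupported:

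- *The percentages are what the trial will see.* They rest on assumed visit schedules, one order per injection and continued ADT. They show what the formula permits.
- *The repeat-triggering sentence is false for Sc.* It says more than once, not at every injection, and it holds for an Sc patient with two target clinic visits. The defect is that it omits the exception for injection-only visits.
- *Orders in the Sc arm predate the note.* The survey offers "More than 7 days before injection" as an answer on when orders are written. An answer option is not evidence that this happens at an Sc site.
- *The order-level ratio should be discarded.* Signed scripts over all orders does say how much prescribing the script reached, structural gaps included. That is a legitimate coverage measure, and signed over assigned would hide it.

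It can also be said that Pilot Data Collection leaves the Table 4 measures to be refined during the pilots, that signed and unsigned notes are tracked anyway, and that an analysis plan might define the terms. These points lessen the problem without removing it. Version 6, dated 10/04/2023, already contains note-assignment steps for the trial sites, and it still carries both the formula and the delivery rule.

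**Conclusion.** The point holds in a limited form. The protocol bars the note from injection-only visits, shows that such visits exist at an Sc trial site, and scores Sc penetration against orders without an exclusion. Unless each order is tied to a discussion visit, which is nowhere stated, the ratio mixes provider uptake with the local injection and visit schedule. It is also not guaranteed to lie between 0 and 100%.

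The size depends on s, which the protocol does not give. With perfect delivery and one note for each remaining order, the ceiling is 1 - s. The 50% and 17% examples correspond to one discussion visit in 6 months with 3-monthly and monthly injections respectively.

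The row is a secondary RE-AIM outcome. The Effectiveness row uses the same denominator, but its numerator is also built from orders, so this mismatch between visits and orders does not carry over to the primary outcome.

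**What to change.** 1. **Uptake.** Report Sc uptake as notes signed over notes assigned. Take the denominator from the study database, where staff record the date each note is assigned. The CPRS progress-note (TIU) report is not a safe source, because the Progress Note section warns that unsigned notes deleted by providers are unlikely to appear in it.
2. **Coverage.** Keep an order-level figure but label it coverage: the share of low-value orders or injections in the window preceded by at least one assigned note. Show injection-only orders separately, and define in Table 4 what counts as an order given and an order stopped.
3. **Repeat triggering.** In Trial Or/Sc Implementation, state that for Sc repeat triggering applies to repeat target clinic visits and not to injection-only visits.

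The cost is a wording change in two places and one extra reported ratio. Assigned notes and their dates are already recorded, as are signed and unsigned notes, and injections are ascertained for the outcomes.
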